Protocol ID	1236
Cinicaltrials.gov ID	NCT04862858
Brief title	Educational Intervention to Increase Select Guideline-recommended Cardioprotective Medications in Patients With Diabetes
Official title	Improving Outcomes in Patients With Comorbid T2DM and ASCVD: Population Health Management Interventions Supporting Guideline-recommended SGLT2i and GLP-1 RA Medications
Date	22 June 2021

TABLE OF CONTENTS

BACKGROUND AND RATIONALE.....	3
STUDY METHODS	4
REFERENCES	14

BACKGROUND AND RATIONALE

Over 34 million individuals in the United States in 2018 were estimated to have diabetes (diagnosed and undiagnosed), with approximately 95% of those individuals having type 2 diabetes mellitus (T2DM).¹ Diabetes increases the risk of developing cardiovascular disease (CVD) and nearly doubles the risk of death from heart disease or stroke.² While CVD is associated with morbidity and mortality in patients with T2DM, the economic impact is also substantial. The median annual healthcare costs per patient with CVD and T2DM has been estimated to be 112% higher compared to patients with T2DM without CVD, hospitalizations driving the costs.³

While there are evidence-based and guideline-recommended therapies for patients with T2DM and atherosclerotic cardiovascular disease (ASCVD) that reduce morbidity and mortality associated with CVD, gaps in treatments exist. Specifically, utilization of sodium-glucose cotransporter-2 inhibitors (SGLT2i) and glucagon-like peptide-1 receptor agonist (GLP-1 RA) medications with proven cardiovascular benefit remains low (<10%),⁴ despite guideline recommendations from the American Diabetes Association (ADA) and American College of Cardiology (ACC) supporting their use.^{5,6} Currently, the products with Food and Drug Administration (FDA) approved/labeled cardiovascular specifically in patients with ASCVD benefit include SGLT2is empagliflozin, canagliflozin, and dapagliflozin, and GLP-1 RAs dulaglutide, liraglutide and injectable semaglutide.

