A Pharmacy Quality Alliance (PQA) measure titled, “Use of Medications to Prevent Major Cardiovascular Events in Persons with Diabetes (CVDM)”, was voted on and approved by the membership in December 2020, is another strategy to help address this noted gap in effective care. However, complementary evidence-based initiatives are needed to communicate benefits of these medications to providers while simultaneously encouraging patients to engage in discussions with providers about their CV risk and ways to reduce future events.

As such, the purpose of this collaborative pilot is to test the impact of a dual educational intervention that includes communication to providers that their identified patients with T2DM and existing ASCVD may be candidates for guideline recommended medications, combined with communication to the identified at-risk patients regarding their CV risk.

STUDY METHODS

Study Objectives

The underutilization of ADA and ACC recommended treatments, specifically SGLT2i and GLP-1 RA medications with CV benefit, have been identified in the literature. In an effort to close this gap in the high-risk population of patients with T2DM and ASCVD, this pilot aims to inform select providers about the recent updates in guidelines regarding optimal treatment and also aims to inform patients about their risk and encourage discussions with providers about how to reduce their future risk of CV events.

Primary Objective

- Evaluate the impact of a dual educational outreach on 6-month frequency of SGLT2i and GLP-1 RA medication initiation by comparing patients and providers who receive and who do not receive the intervention.

Secondary Objectives

- Evaluate the impact of a dual educational outreach on 12-month frequency of SGLT2i and GLP-1 RA medication initiation by comparing patients and providers who receive and who do not receive the intervention.
- Evaluate the adherence and persistence to SGLT2i and GLP-1 RA medications 6-months after initiation. (Note: this outcome may also be assessed at 12-months post-initiation based on results of 6-month measure)

The hypothesis is that there will be a significantly greater (2% absolute increase) initiation of SGLT2i and GLP-1 RA medications with CV benefit among those who receive the educational outreach and message as compared to those who do not receive the intervention.

Data Source

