After the mailing (or fax) has been sent, a follow-up call to providers and patients will be conducted to ensure the message was received, reiterate the content of the initial outreach, and encourage discussions between patients and providers about CV risk reduction strategies. This call will be planned to take place within a few weeks (~3 weeks) from the initial mailing. While it will be requested to speak directly with the provider, nurses or other office staff may receive the call. Up to three call attempts will be made, with general messages being left asking for a return call if a voicemail is reached.

Three months after the initial outreach, another mailed/faxed communication will be sent to the providers reiterating the messaging from the first two communications, and including the list of patients who are still eligible for treatment and also noting those who have received treatment. The patients will also receive another direct mail communication approximately 3 months after the initial outreach reiterating the messaging from the first two communications.

The primary outcome for this study is the initiation of guideline-recommended SGLT2i or GLP-1 RA medications with CV benefit (excluding combination products) within 6-months of the initial outreach. Secondary outcomes include: 1) initiation of the medications of interest (excluding combination products) within 12 months of the initial outreach; 2) initiation of guideline-recommended SGLT2i or GLP-1 RA medications with CV benefit (including combination products) within 6-months of the initial outreach; 3) initiation of guideline-recommended SGLT2i or GLP-1 RA medications with CV benefit (including combination products) within 12-months of the initial outreach; and 4) adherence to SGLT2i or GLP-1 RA medications 6-months post-initiation; and 5) persistence to SGLT2i or GLP-1 RA medications 6-months post-initiation.

Identification and randomization: July 2021 (date on which data extraction begins)

Index event: date of first outreach to patients/providers (August 2021)

Second outreach (calls): start 3 weeks post-index

Third outreach (mailing/fax): starts 3 months post-index

[figure not shown]
Pre-identification and pre-index: 12-months continuous enrollment

Post-index: none

Follow-up: the primary outcome will be evaluated at 6-months and a secondary outcome will be utilization at 12 months post-index

Full data period: up to 2 years pre-index to 12-months post-index (July 2019 – August 2022)

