
Figure. Study design

The inclusion and exclusion criteria, below, will be utilized to identify the eligible patient population.

Patient

- Patients with T2DM defined as ≥ 2 outpatient diagnoses of T2DM in any position on separate days; OR ≥ 1 inpatient diagnosis T2DM in any position; OR ≥ 1 outpatient diagnosis in any position AND ≥ 1 medication claim for T2DM
- ≥ 1 diagnosis code for ASCVD (coronary artery disease diagnoses or procedures, cerebrovascular disease, peripheral artery disease of atherosclerotic origin) on any claim type in any position within the 24-month period prior to identification
- Enrolled in a Humana Medicare Advantage Prescription Drug plan with ≥ 12 months pre-identification continuous enrollment (no more than a 31 day gap) as of the identification date and currently enrolled as of the identification date
- Age 18-85 years at time of identification
- Patients residing in Kentucky (KY), West Virginia (WV), Pennsylvania (PA), and 6 counties in south New Jersey (NJ) (Burlington, Camden, Cumberland, Gloucester, Mercer, Salem) (United States)

Provider

- Primary care providers of the identified patients

Exclusion Criteria:

Patients

- ≥ 1 diagnosis or procedure code for end-stage kidney disease, renal transplant, dialysis or kidney failure
- Any hospice or long-term care residence
- ≥ 1 code for pregnancy/childbirth
- Patients with any use of SGLT2i or GLP-1 RA medications in the pre-identification period
- Patients without an attributed primary care provider
- Patients on do not contact lists
- Patients without valid addresses and telephone numbers
- Patients with ≥ 1 diagnosis for type 1 diabetes pre-identification

Primary care providers

- Providers on do not contact lists
- Providers without valid fax/mailing address and phone number
- Providers with <3 and >50 eligible patients
- Providers with eligible patients across multiple risk arrangements

Specialist providers will be included in the outreach if there is an indication from the claims data that the identified patient has had an encounter with a cardiologist and/or endocrinologist up to 24-months pre-identification. These providers will not be contacted if on do not contact lists or if there are no valid fax/mailing address and phone numbers for those providers. Only specialist providers with <50 eligible patients will be included.

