The eligible patients and providers will be identified based on the inclusion/exclusion criteria. The attributed providers for each patient will be identified. For the primary care providers, the risk arrangement in which they are currently contracted, will be identified. Providers will be equally randomized via a simple random sample across (stratified) non-value based (e.g., fee-for service) or value-based (i.e., path-to-value and full value) arrangements between the intervention and control arms. All of the eligible patients for each identified primary care provider will be included in the same study cohort (i.e., either all control or all intervention).

Demographic, clinical and socioeconomic characteristics in the 12-month baseline period for patients and providers will be described (n (%), mean [standard deviation (SD)], median [interquartile range (IQR)], minimum, maximum). To ensure representativeness of the randomized sample, the sample will be compared to that of the sampling frame using standardized differences. The comparability between the intervention and control arms will also be assessed with standardized differences. Standardized differences will be assessed for each variable using the following example formulae¹¹:

Continuous variables:

$$d = \frac{\bar{X}_{group1} - \bar{X}_{group2+3}}{\sqrt{\frac{s^2_{group1} + s^2_{group2+3}}{2}}}$$

Binary variables:

$$d = \frac{\hat{p}_{group1} - \hat{p}_{group2+3}}{\sqrt{\frac{\hat{p}_{group1}(1 - \hat{p}_{group1}) + \hat{p}_{group2+3}(1 - \hat{p}_{group2+3})}{2}}}$$

where \bar{X} represents the mean of the covariate, s^2 represents the sample variance of \bar{X} , and \hat{p} represents the prevalence of that covariate. Variables with a standardized difference less than 0.1 will be considered balanced.

The primary analytic cohort for this aim will consist of the patients/providers randomized to the control arm and the patients/providers randomized to the intervention arm who received at least the first outreach (i.e., no returned mailings/faxes).

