The proportion of patients filling at least one pharmacy prescription for a SGLT2i or GLP-1 RA medication with CV benefit within 6-months of the intervention initiation will be compared. The unadjusted proportion of patients initiating the medications in each arm will be described (n [%]). A generalized linear mixed model (GLMM) with a binomial distribution and logit link will then be used to account for the clustering of patients within providers without any adjustment for covariates, except the stratification variable (random cluster effects).¹²⁻¹⁴ Parameter estimates, odds ratios (ORs), standard error, 95% confidence intervals (CI) and p-values will be reported. If significant differences are detected between the patients in the intervention and control groups, greater than 0.1 in standardized difference, then adjustment for confounding, to minimize bias, utilizing regression models would be required as an additional analysis (e.g., covariate adjustment). For categorical variables with missing values, a missing category will be added. For continuous variables with missing values, the values will be categorized with a missing category added. This will allow for all patients to be retained in the analyses. No imputation will be conducted.

Secondary Objectives

Evaluate the impact of a dual educational outreach on 12-month frequency of SGLT2i and GLP-1 RA medication initiation by comparing patients and providers who receive and who do not receive the intervention.

The 12-month frequency of the SGLT2i and GLP-1 RA medication initiation with CV

benefit will be assessed using the same analytic cohorts and methodologies, as described above.

Evaluate the adherence and persistence to SGLT2i and GLP-1 RA medications 6-months after initiation.

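### The primary cohort removes intervention-arm patients and providers with returned mail or fax but keeps every control, so the primary comparison is not the randomised one and probably favours the intervention

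*Combined protocol and SAP*

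**What the plan says.** Primary care providers are the unit of randomisation, allocated equally to the two arms within value-based and non-value-based strata: "Providers will be equally randomized via a simple random sample across (stratified" by contracting arrangement). Study Design and the SAP both say that all eligible patients of a sampled provider enter that provider's arm.

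The SAP then defines the population for the primary analysis. On the control side there is no further condition: "The primary analytic cohort for this aim will consist of the patients/providers randomized to the control arm". On the intervention side the cohort is limited to "patients/providers randomized to the intervention arm who received at least the first outreach (i.e., no returned mailings/faxes").

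Under Secondary Objectives, 12-month initiation "will be assessed using the same analytic cohorts and methodologies, as described above", so the restriction carries over.

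Three other provisions bear on the point:

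- The exclusion criteria remove, before randomisation and in both arms, "Patients without valid addresses and telephone numbers", and likewise providers without valid contact details.
- A failed fax is replaced by a mailing.
- The study timeline requires no enrolment after the index date: "Post-index: none".

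**The concern.** Randomisation makes the arms comparable only if the analysis keeps the groups it created. Here one arm is trimmed by an event that cannot be observed in the other: a control cannot have a returned letter, so the controls who would have had one cannot be identified and stay in.

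The trimmed patients are unlikely to be typical. All had passed a contact-details screen and were enrolled at identification. A letter that still comes back suggests a move, a death or a departure from the plan, and such patients seldom generate a pharmacy claim. Because no post-index enrolment is required, the matching controls remain in the denominator and count mostly as non-initiators. The Limitations section itself says that outcomes of patients who leave the plan may be misclassified for want of data.

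Two things are at stake. The rule can produce an apparent benefit when there is none. It also removes the dilution caused by undeliverable outreach, which is part of what a roll-out would deliver, and the Limitations section foresees using this pilot to scale similar efforts.

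**Working it through.** The documents state no sample size, power, return rate or control initiation rate, so there is no planned figure to reproduce. What follows shows how large the distortion could be.

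**Inputs**

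- Hypothesised effect: 2 percentage points absolute (Study Objectives).
- Control 6-month initiation, p: assumed 6%, with 4% to 10% also examined. The only nearby figure is current use below 10% (Background), which is prevalence of use, not initiation.
- Share of the intervention arm dropped, r: assumed, 1% to 15%.
- Initiation rate among those dropped, q: assumed, from 0 to half of p, with q = p and q = 1.5p as checks.
- Two-sided 5% test: assumed from the planned 95% confidence intervals.
- Patients per arm: assumed 3,444. This is about 2,551 for 80% power to detect 6% versus 8%, times an assumed design effect of 1.35 (2,551 × 1.35 ≈ 3,444).

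**Bias with no true effect**

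The analysed intervention rate is (p − r·q)/(1 − r), so

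bias = r·(p − q)/(1 − r).

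Example with p = 6% and r = 10%:

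- q = 3%: (0.06 − 0.10 × 0.03)/0.90 = 0.057/0.90 = 6.33%, bias +0.33 points.
- q = 0: 0.06/0.90 = 6.67%, bias +0.67 points.

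**Type I error**

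The standard error is √{1.35 × [p(1−p)/n + p₁(1−p₁)/(n(1−r))]}, where p₁ is the analysed intervention rate. At r = 10% and q = 0 it is 0.701 points. The shift is 0.667/0.701 = 0.95 standard errors, and the two-sided rejection rate is 15.8%.

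All rows use p = 6%:

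| Dropped, r | Bias, q = 0.5p | Type I error | Bias, q = 0 | Type I error |
|---|---|---|---|---|
| 1% | 0.03 | 5.0% | 0.06 | 5.1% |
| 2% | 0.06 | 5.1% | 0.12 | 5.4% |
| 3% | 0.09 | 5.2% | 0.19 | 5.9% |
| 5% | 0.16 | 5.6% | 0.32 | 7.5% |
| 10% | 0.33 | 7.7% | 0.67 | 15.8% |
| 15% | 0.53 | 11.6% | 1.06 | 31.0% |

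For r from 5% to 15% the bias is therefore 0.16 to 1.06 points, or 0.16/2 = 8% to 1.06/2 = 53% of the hypothesised effect. Over p from 4% to 10% and r from 2% to 15%, with q between 0 and 0.5p, it runs from 0.04 to 1.76 points.

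The direction depends on q. At q = p the bias is zero for any r. At q = 1.5p and r = 10% it is −0.33 points.

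The design effect of 1.35 has little influence on these error rates, because n was scaled up by the same factor. A study with more information than assumed would show more inflation, and one with less would show less.

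**With a true effect**

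Suppose outreach adds 2 points in those reached and nothing in those not reached, with p = 6%, r = 10% and q = 0.5p. The as-randomised effect is 0.90 × 2 = 1.80 points. The planned cohort would show 2 + 0.33 = 2.33 points.

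**The case against.** The strongest reply is that the return rate may be very low. Both arms are screened for valid contact details, patients must be enrolled at identification, first outreach is planned for August 2021 after July identification, and a failed fax leads to a mailing. At 1–3% dropped, the bias is at most 0.19 points and the type I error at most 5.9%. The larger figures need 10–15% undeliverable after that screen. This stands as a comment on size: material distortion is possible, not demonstrated.

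The direction is also an inference. Every scenario with q below p favours the intervention, and the reverse cannot be excluded. The account of movers, deaths and leavers concerns patients and says little about providers whose mail is returned. This also stands, and it is why the conclusion says probably.

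The plan has partial safeguards. An adjusted additional analysis follows if a standardised difference exceeds 0.1, and the Limitations section promises sensitivity analyses for outcome misclassification, including disenrolment. Neither restores the randomised groups. The first is conditional and limited to measured baseline variables. The second is unspecified and does not address this exclusion. The SAP sentence about retaining all patients concerns missing covariate values only.

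Finally, the objective is worded in terms of receiving or not receiving the intervention, so a receipt-based question could be called prespecified. Even so, recipients would need to be compared with controls who would have received it, and the plan has no such group.

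Loss of whole clusters is an ambiguity rather than a demonstrated harm. The text does not say whether a returned primary care communication removes all of that provider's 3 to 50 patients, or whether a returned specialist communication counts.

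**Conclusion.** The concern holds. It is certain from the text that the only primary comparison specified, and the 12-month comparison that reuses its cohorts, applies a post-randomisation exclusion to one arm with no as-randomised analysis behind it. That needs correcting whatever the return rate turns out to be.

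The direction is probably in favour of the intervention, provided that those dropped initiate less often than average. The size cannot be determined from the documents. On the stated assumptions it ranges from negligible at returns of 1–3% to about half the hypothesised effect at 15% returned with no initiation among those dropped.

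**What to change.** Define the primary analysis cohort as all eligible patients of all randomised primary care providers, analysed in the arm assigned regardless of delivery status, for both the 6-month and 12-month outcomes. This removes this selection bias for any return rate and any initiation rate among those not reached.

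Keep the received-first-outreach cohort as a labelled sensitivity analysis. For it, state whether a returned provider communication removes that provider's patients, and whether specialist returns count. Report the share of returned mailings and faxes separately for patients and providers.

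The cost is SAP wording only: outcomes come from claims already held for every randomised patient, so no further data collection is needed. The estimated effect may be somewhat smaller because unreached patients are included. If outreach has no effect in them, a 2-point effect in those reached becomes 1.96 points at 2% returned and 1.80 points at 10%.

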2. Adherence and persistence to guideline-based SGLT2i or GLP-1 RA medications [Time Frame: 6-months] Adherence and persistence to SGLT2i or GLP-1 RA medications with cardiovascular benefit (excluding combination products)

3. Guideline-based SGLT2i or GLP-1 RA medication initiation (including combination products)
[Time Frame: 6-months]: Proportion of patients who have ≥ 1 pharmacy claim for SGLT2i or GLP-1 RA medications with cardiovascular benefit (including combination products)

4. Guideline-based SGLT2i or GLP-1 RA medication initiation (including combination products)
[Time Frame: 12-months]: Proportion of patients who have ≥ 1 pharmacy claim for SGLT2i or GLP-1 RA medications with cardiovascular benefit (including combination products)

Baseline covariates:

- Demographics
 - Age
 - Sex
 - Race (as available; Black, White, other, unknown/missing)
 - Population density (e.g., rural, urban, suburban)
 - Chronic special needs plan enrollment (as available)
- Clinical characteristics
 - Elixhauser comorbidity index (based on medical claims)⁷⁻⁹
 - RxRisk V (comorbidity index based on medications as proxy)¹⁰
 - Prior MI, stroke, revascularizations
 - Number of unique medications
 - Use and type of antihyperglycemic medications (by class)
 - Use and type of cardiovascular medications (by class)
 - Indication of prior or current tobacco use
 - Indication of obesity and/or body mass index (BMI)

- Laboratory values (as available) (cholesterol, HbA1c, serum creatinine)
- All-cause healthcare resource utilization
 - Inpatient hospitalization
 - Total length of stay for hospitalizations
 - Emergency department visits
 - Provider encounters
 - Other outpatient visits (procedures, tests, imaging, durable medical equipment, other services, and unclassified)
- All-cause costs

Provider characteristics

- Value-based care arrangement for primary care providers
- Provider information (e.g., practice size, as available)

Statistical Analysis Plan

Primary Objective

Evaluate the impact of a dual educational outreach on 6-month frequency of SGLT2i and GLP-1 RA medication initiation by comparing patients and providers who receive and who do not receive the intervention.

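### Continuous covariates with gaps are cut into categories, which leaves part of the observed imbalance in the adjusted additional analysis; a pre-specified spline with a missing indicator keeps the same patients and leaves less

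*Combined protocol and SAP*

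**What the plan says.** All of this is in the combined document, under Statistical Analysis Plan, Primary Objective, unless noted.

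- The main model is a logit mixed model fitted "without any adjustment for covariates, except the stratification variable (random cluster effects").
- Covariate adjustment comes in only if the arms differ by an amount "greater than 0.1 in standardized difference, then adjustment for confounding, to minimize bias, utilizing regression models would be required as an additional analysis". Balance is judged variable by variable: "Variables with a standardized difference less than 0.1 will be considered balanced". For a continuous variable the measure is the difference in means divided by the pooled SD.
- Missing covariate values: "For categorical variables with missing values, a missing category will be added". Then: "For continuous variables with missing values, the values will be categorized with a missing category added". The reason follows: "This will allow for all patients to be retained in the analyses". The paragraph closes with "No imputation will be conducted".
- The list of baseline covariates includes "Laboratory values (as available) (cholesterol, HbA1c, serum creatinine"), so gaps in these are expected. BMI may be a further case, if it is used as a number rather than as an obesity flag.

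The SAP gives no number of categories, no cut-points, no functional form for continuous covariates and no expected missing rate.

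**The concern.** Read as written, a gap in some patients' HbA1c turns every patient's HbA1c into a category. Differences between arms within a category then go unadjusted. The plan would detect imbalance on the continuous scale and correct it on a coarser one, in an analysis whose declared purpose is to reduce bias.

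The reason given does not call for this, since keeping all patients needs only some code for the missing values. With the number of groups and the cut-points open, the amount of imbalance left is also undetermined before the data are seen. What is at stake is the quality of a supporting analysis, not the main estimate.

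**Working it through.** **Inputs.** The plan has no figure to reproduce here. From the SAP: the categorising rule, the 0.1 balance limit and the hypothesised 2-point absolute increase. Assumed: the shape of the covariate, its effect, the size of the imbalance, the missing rate (1%, 30% or 50%, completely at random) and 8% initiation in controls.

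**Step 1: patients with observed values.** For a standard normal covariate with a linear effect and a small mean shift between arms, K equal groups remove a share f equal to the mean of the squared group means. For K = 2 the group means are ±√(2/π) = ±0.798, so f = 0.637. For K = 3, 4 and 5, f = 0.793, 0.861 and 0.897. Unequal cuts can do worse: a single cut at +1 SD removes 44%.

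**Step 2: add the patients with missing values.** If a fraction m is missing completely at random, those patients are unadjusted under either method. The share left is m + (1 − m)(1 − f).

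| Method | Observed patients: 1 − f | m = 30% | m = 50% |
|---|---|---|---|
| 2 groups | 36% | 55% | 68% |
| 3 groups | 21% | 44% | 60% |
| 4 groups | 14% | 40% | 57% |
| 5 groups | 10% | 37% | 55% |
| Continuous, right form, with indicator | about 0% | 30% | 50% |

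**Step 3: logistic scale.** Logistic models were fitted to expected outcomes with no true treatment effect, a 0.2 SD imbalance, a log-odds slope of 0.5 per SD and no provider clustering. Unadjusted, the spurious log-OR is about 0.10. After adjustment it is:

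| Covariate, missing | 2 groups | 3 | 4 | 5 | Linear term + indicator |
|---|---|---|---|---|---|
| Normal, 1% | 0.039 | 0.023 | 0.016 | 0.013 | 0.001 |
| Normal, 30% | 0.056 | 0.045 | 0.040 | 0.038 | 0.029 |
| Normal, 50% | 0.068 | 0.061 | 0.057 | 0.055 | 0.050 |
| Lognormal, effect on log scale, 30% | 0.056 | 0.045 | 0.041 | 0.038 | 0.058 |

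The last row shows that an untransformed linear term can do worse than any of the categorisations. In that setting a 5-knot restricted cubic spline with the indicator left 0.028 to 0.033 over separate simulation runs, and 0.031 when evaluated on a fixed grid without sampling noise. The correct log form left 0.030. The grid evaluation agreed with the other entries to within about 0.002.

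**Step 4: scale.** With 8% assumed in controls, 8% against 10% is a log-OR of ln[(0.10/0.90)/(0.08/0.92)] = 0.245. At 30% missing with a normal covariate, the gain over categories is 0.056 − 0.029 = 0.027 for 2 groups and 0.038 − 0.029 = 0.009 for 5. That is about 11% and 4% of 0.245.

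**The case against.** The strongest case against is that this is a small matter in a secondary place. The adjusted model is a conditional additional analysis, and the covariate that triggers it may be a complete one such as age. With three or more groups the gain at 30% missing is at most 0.045 − 0.029 = 0.016 on the log-OR scale. An assumed 0.15 SD difference among observed patients would fall to 0.15 × 0.363 = 0.055 SD after a median split, inside the plan's own 0.1 limit. To leave more than 0.1 SD, the starting imbalance would have to exceed 0.1/0.363 = 0.28 SD with 2 groups or 0.1/0.103 = 0.97 SD with 5. If the true effect is a step at the median, categories and a continuous term do about equally well (0.022 each for 2 groups and a linear term at 30% missing). All of this stands, and it makes the point minor.

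A further objection is that a mean fill breaches the commitment not to impute. This is a matter of wording: the indicator absorbs the filled constant, so its value does not affect the treatment estimate.

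Three stronger readings are tempting and are not supported:

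- *That the alternative loses nothing.* Imbalance among patients with missing values stays under both methods, and the advantage depends on functional form.
- *That baseline missingness cannot depend on arm.* This holds for the cohort as randomised. The primary analytic cohort restricts only the intervention arm, to those who received the first outreach, so missingness among analysed patients may differ by arm. The plan's missing category has the same limit.
- *That the main result is affected.* The main model carries no covariate to which the rule applies.

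**Conclusion.** The point holds as a small, inexpensive improvement. Categorising is unnecessary for the purpose stated. Among patients with observed values it leaves about 36% down to 10% of the imbalance for 2 to 5 equal groups, given a normal covariate with a linear effect. The actual figure cannot be fixed from the documents, because the groups, cut-points and missing rates are not stated. A spline with a missing indicator left less bias than 2 to 5 categories in the normal and skewed settings where it was tried. The log-OR figures rest on the assumed 8% initiation, 0.2 SD imbalance and slope of 0.5, and they ignore clustering by provider.

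**What to change.** Replace the sentence on continuous variables with:

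> Continuous covariates with missing values will be kept continuous using a restricted cubic spline with pre-specified knots at quantiles of the observed values; missing values will be set to the overall observed mean, calculated without regard to arm, and a missing indicator will be added to the model.

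Reword the last sentence of that paragraph to: *No model-based imputation will be conducted.* Keep the missing category for categorical variables. Do not offer a plain linear term as an equal option.

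The cost is one replaced SAP sentence, one changed phrase and a few extra degrees of freedom per affected covariate. No patient is lost and the main model does not change. The indicator still cannot be guaranteed independent of arm in the received-outreach cohort, a limit it shares with the present rule.
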